**PHASE 3B/4 RANDOMIZED SAFETY ENDPOINT STUDY OF 2 DOSES OF
TOFACITINIB IN COMPARISON TO A TUMOR NECROSIS FACTOR (TNF)
INHIBITOR IN SUBJECTS WITH RHEUMATOID ARTHRITIS**

Compound:	CP-690,550-10
Compound Name:	Tofacitinib citrate
US IND Number:	CCI
European Clinical Trial Database (EudraCT) Number:	2013-003177-99
Protocol Number:	A3921133
Phase:	Phase 3b/4

This document contains confidential information belonging to Pfizer. Except as otherwise agreed to in writing, by accepting or reviewing this document, you agree to hold this information in confidence and not copy or disclose it to others (except where required by applicable law) or use it for unauthorized purposes. In the event of any actual or suspected breach of this obligation, Pfizer must be promptly notified.

Document History

Document	Version Date	Summary of Changes
Original protocol	25-Apr-2013	N/A
Amendment 1	10-Jul-2013	
Prior to initiation of the study and in response to US FDA comments and recommendations, the following changes were made to the study protocol:
 
 1. Reduced the study from 8 years to 5 years. 2. Increased N from 3900 to approximately 4000. 3. Enriched the study population to include only patients ≥ 50 yrs with ≥ 6 painful/tender joints and ≥ 6 swollen joints and who have at least one risk factor for cardiovascular disease. 4. Eliminated the double-blind substudy (all drug supplies are open-label). 5. Changed the comparator from all adalimumab to adalimumab in US, Puerto Rico and Canada with etanercept in the rest of world. 6. Removed the need for blinded joint assessors. 7. Have all patients on background methotrexate. 8. Allow prior use of biologic DMARDs with appropriate washout, unless intolerant or unresponsive to previous use. 9. Added Section 'Immunizations' live or live-attenuated vaccines should not be given concurrently with study medication. 10. Eliminated the 2-week visit. 11. Reduced joint counts from 66/68 to 28 at every visit. 12. Aligned the contraceptive requirements with the removal of methotrexate as a comparator. 13. Removed the following PROs: MOS Sleep Scale, FACIT-Fatigue, and RA Healthcare Resource Utilization Questionnaires and reduced the frequency of SF-36, EuroQol EQ-5D, and Work Productivity and Activity Impairment (WPAI) Questionnaires.

Document	Version Date	Summary of Changes
		
 14. Eliminated routine urinalysis testing, except at Screening Visit. 15. Eliminated routine ECGs, except at Screening Visit and End of Study Visit. 16. Removed laboratory testing not used in safety evaluation of either tofacitinib or TNFi's; CRP will not be blinded. 17. Monitoring and discontinuation criteria is aligned with the US approved labeling. 18. There will be no interim analyses of the data, only end of study analysis. 19. The study will be stopped on recommendation of the Steering Committee and only after consultation with the US FDA. 20. The Steering Committee will maintain Performance Standards, review metrics and implement corrective actions.
Amendment 2	16-Aug-2013	
 1. Typographical corrections and clarifications 2. Added Japan-specific screening and monitoring requirements. 3. Added reference for endpoint definitions and clarification regarding endpoint composite for MACE. 4. Added cholestyramine or activated charcoal elimination procedure to reduce leflunomide washout to 4 weeks.
Amendment 3	20-Nov-2013	
 1. Typographical corrections and clarifications. 2. Changes to reporting processes for the primary safety endpoints to limit their inclusion in AE tables reviewed outside the blinded Steering Committee. 3. Addition of a washout period for rituximab as a prohibited concomitant DMARD. 4. Removed Japan-specific screening and monitoring requirements as Japan will not be participating in this study.
Amendment 4	30-Jan-2014	
 1. Typographical corrections. 2. Addition of voriconazole as a prohibited concomitant medication. 3. Clarification of the role of the OTIS registry in the US only and follow-up of pregnancies.

Document	Version Date	Summary of Changes
		
 4. Remove the requirement for adalimumab/etanercept dispensing at Visit 2, as drug supply to sites will be sufficient to supply drug at Visit 1 and then at Visit 3. 5. Clarification of the respective roles of the Steering Committee and the DMC and provision to allow the DMC to review adjudicated and non-adjudicated primary endpoint data in an unblinded manner at the explicit request of the DMC.
Amendment 5	30-Mar-2014	
 1. In Section 1.2 added reference to Section 7.8 of the XELJANZ Investigator Brochure as the section that contains reference safety information. 2. Added Appendix 4 with Sweden-specific text for exclusion criteria, triggered event criteria, and the addition of the Overall Risk-Benefit Assessment (ORBA) with references to the appendix in the body of the protocol at the request of the Swedish competent authority.
Amendment 6	30-May-2014	
 1. Added Appendix 5 with and Czech Republic, Spain and United Kingdom-specific text for exclusion criteria, triggered event criteria, and additional laboratory testing (lymphocyte subset testing) at the request of the respective competent authorities for each country.
Amendment 7	12-Jan-2015	
 1. Added Appendix 6 with Canada specific text regarding the use of 2 methods of contraception, one highly effective and one effective method as per the request of the competent authority.
Amendment 8		
 1. Reduced treatment in the tofacitinib 10 mg BID arm to 5 mg BID in response to a recommendation from the Data Safety Monitoring Board for a safety signal. 2. Added requirement for all subjects to be provided a consent addendum, which they will be required to sign agreeing to continue in the study. 3. Deep vein thrombosis, pulmonary emboli, arterial thrombosis and arterial emboli were added to the CV adjudication charter and are noted as additional events to be adjudicated.

Document	Version Date	Summary of Changes
		4. Added mandatory revised privacy text. 5. Removed Appendix 4 as no subjects were screened or randomized in Sweden and enrollment is closed.

This amendment incorporates all revisions to date, including amendments made at the request of country health authorities, institutional review boards/ethics committees (IRBs/ECs), etc.

PROTOCOL SUMMARY

As a commitment to the United States Food and Drug Administration (US FDA), this Post Authorization Safety Study (PASS) will evaluate the safety of tofacitinib 5 mg twice daily (BID) and tofacitinib 10 mg BID compared to a tumor necrosis factor inhibitor (TNFi).

The primary objective of this endpoint study is to evaluate the safety of tofacitinib at two doses versus a TNFi; the co-primary endpoints are adjudicated major adverse cardiovascular events (MACE) and adjudicated malignancies excluding non-melanoma skin cancers during study participation.

The study will be declared complete when all of the following conditions are met:

- At least 1500 subjects have been followed for 3 years.
- The targeted number of MACE is observed.
- The targeted number of malignancies, excluding non-melanoma skin cancers, is observed.

To achieve all of these conditions, it is expected that the study will include approximately 4000 subjects, recruited over 3 years and the total duration of the study will be approximately 5 years after the first subject is randomized.

The Steering Committee will consider the ongoing accumulation of the adjudicated primary endpoint events and performance standard metrics and may determine that sufficient events have occurred to assess the primary objectives of the study or that it is not feasible to continue the trial in pursuit of these objectives. These determinations by the Steering Committee will be made in accordance with pre-specified rules documented in the Steering Committee Charter and in the Statistical Analysis Plan and following consultations with the US FDA, and could result in recommendations for changes to the study design, including changes in number of subjects studied or duration of study.

Subject population

Adult subjects who are 50 years of age or older, with moderately or severely active rheumatoid arthritis who have had an inadequate response to methotrexate alone and who have certain risk factors for cardiovascular disease will be enrolled in this study. A minimum of approximately 4000 subjects will be enrolled in the study.

Assessments

The following assessments will be used to evaluate safety:

- Changes in physical assessments, including weight and vital signs.
- AE reporting, incidence and severity.

- Incidence and severity of safety laboratory abnormalities.
- Adherence to contraceptive use.
- Adherence to protocol requirements.
- Concomitant medication review.
- Review of eligibility to continue study drug.

The following assessments will be used to evaluate efficacy:

- 28 joint counts.
- Patient Global Assessment.
- Patient Assessment of Pain.
- Physician Global Assessment.
- C-reactive Protein (CRP).
- A number of patient reported outcomes, including the Health Assessment Questionnaire – Disability Index (HAQ-DI).

Treatments

All subjects will be enrolled on their previously prescribed dose of methotrexate and will be randomly assigned to one of three active treatment arms in the study:

- Tofacitinib 5 mg BID.
- Tofacitinib 10 mg BID.*
- TNFi: adalimumab 40 mg subcutaneous (SC) injection every other week in the United States, Puerto Rico and Canada; etanercept 50 mg SC injection weekly in all other countries.

* In response to new safety information about tofacitinib that was provided to Study A3921133 investigators on 19 February 2019, investigators were notified to verbally inform subjects randomized to tofacitinib 10 mg BID to reduce the dose of tofacitinib to 5 mg BID within 7 calendar days of this notification, secure their verbal agreement to continue in the study, and if they agreed, reduce their dose of tofacitinib to 5 mg BID for the remainder of the study. Tofacitinib is supplied as 5 mg tablets, which allowed subjects to decrease from their previous dose of 2 tablets twice daily to 1 tablet twice daily.

Adjustments to methotrexate and other background medications will be allowed during the study with provisions to allow subjects who are not adequately treated with study drug to switch to standard of care while remaining in the study.

The study will be open-label and the randomization scheme for the study population (approximately 4000 subjects) will be in a ratio of 1:1:1 with approximately 1300 subjects randomized to tofacitinib 5 mg BID; approximately 1300 subjects randomized to tofacitinib 10 mg BID (subjects are switched to 5 mg BID per Amendment 8); and approximately 1300 subjects randomized to a TNFi.

Safety Analysis

The safety analysis will include all subjects in the study.

The primary statistical safety objective is the estimation of the hazard ratios relative to the TNF inhibitor control for the two tofacitinib doses combined and for each dose of tofacitinib separately for the co-primary events of major adverse cardiovascular events (MACE) and malignancies excluding non-melanoma skin cancers. Analyses of primary safety endpoints will be based upon adjudicated events.

Both total time (ITT) and on treatment analyses of the main safety endpoints will be conducted. The on treatment analysis for MACE will censor subjects who cross over from tofacitinib or adalimumab to standard of care at 60 days after standard of care is initiated. The principal analysis for malignancies will not censor for subjects crossing to standard of care (ie, will be the total time analysis).

Secondary safety endpoints will be summarized according to treatment received at the time of the event.

For the purposes of statistical analyses, subjects who were randomized to tofacitinib 10 mg BID will be maintained in the tofacitinib 10 mg BID treatment arm after reducing the dose of tofacitinib to 5 mg BID.

SCHEDULE OF ACTIVITIES BY VISIT (SCREENING – MONTH 6)

The Schedule of Activities table provides an overview of the protocol visits and procedures. Refer to [Study Procedures](#) and [Assessments](#) sections of the protocol for detailed information on each procedure and assessment required for compliance with the protocol.

The investigator may schedule unplanned visits in addition to those listed on the schedule of activities, in order to conduct assessments required to protect the well-being of the subject.

Protocol Activities – Screening to Month 6	Screen	Visit 1 Day 1	Visit 2 Month ^f 2	Visit 3 Month ^f 3	Visit 4 Month ^f 6
Visit Windows (see Section 6.2.1 for further detail)	NA	See 6.2.1	±2 weeks	±1.5 months	±1.5 months
Informed Consent	X				
Medical History and Confirm Diagnosis	X				
Physical Examination, including height	X				
Assessment of New Physical Findings		X	X	X	X
Weight, Vital Signs	X	X	X	X	X
Inclusion/Exclusion criteria	X	X			
Blood Chemistry ^a , Hematology ^a	X	X	X	X	X
C-reactive Protein (CRP)	X	X	X	X	X
Banked Biospecimens		X			
HIV Serology, HBsAg, HBcAb, HBsAb ^b	X				
HCV Ab, HCV RNA ^c	X				
Lipid Profile (fasting)	X	X	X		
Pregnancy test ^d	X	X	X	X	X
QuantiFERON Gold®™ In-Tube Test	X				
Rheumatoid Factor	X				
Anti-cyclic citrullinated peptide (anti-CCP)	X				
Urinalysis	X				
Chest X-ray	X				
ECG	X				
Randomization		X			
Study Medication Dispensing		X		X	X
Contraceptive Use Documentation	X	X	X	X	X
Joint Count (28)	X	X	X	X	X
Patient Assessment of Arthritis Pain		X	X	X	X
Patient Global Assessment of Arthritis		X	X	X	X
Physician Global Assessment of Arthritis		X	X	X	X
HAQ-DI		X	X	X	X
SF-36 (Version 2, Acute)		X		X	X
EuroQol EQ-5D		X		X	X
Work Productivity and Activity Impairment (WPAI)		X		X	X
Safety Assessment/ AE Reporting		X	X	X	X
Concomitant Medication Review	X	X	X	X	X
End of Study Assessment					

^{a.} Re-testing of abnormal laboratories may be required (see [Section 7.15](#)).

^{b.} See Exclusion Criteria [4e](#) and [4f](#) for details.

^{c.} See Exclusion Criteria [4g](#) for details.

^{d.} Pregnancy tests may also be repeated as per request of IRB/IECs or if required by local regulations.

^{e.} History of concomitant medications at Screening includes a history of prior DMARD treatment.

^{f.} Calendar months.

SCHEDULE OF ACTIVITIES BY VISIT (MONTH 9 – END OF STUDY)

Visits are outlined through Month 60, but will continue sequentially until the end of study is declared, at which time all subjects will be required to return for an End of Study Visit.

Protocol Activities – Months 9 to 60 and End of Study Follow-up Visit	Visits 5, 9, 13, 17, 21 [Months ^f 9, 21, 33,45, 57]	Visit 6, 10, 14, 18, 22 [Months ^f 12, 24, 36, 48, 60]	Visits 7, 11, 15, 19 [Months ^f 15, 27, 39, 51]	Visits 8, 12, 16, 20 [Months ^f 18, 30, 42, 54]	End of Study Visit	End of Study Follow Up^g
Visit Windows (see Section 6.2.1)	±1.5 months	±1.5 months	±1.5 months	±1.5 months	±1.0 months	+0.5 months
Assessment of New Physical Findings	X	X	X	X	X	X
Weight, Vital Signs	X	X	X	X	X	X
Blood Chemistry ^a , Hematology ^a	X	X	X	X	X	
C-reactive Protein (CRP)	X	X	X	X	X	
Banked Biospecimens		X ^b			X	
Lipid Profile (fasting)		X			X	
Pregnancy test ^c	X	X	X	X	X	X
QuantiFERON Gold®™ In-Tube Test		X ^d				
Chest X-ray		X ^e			X ^e	
ECG					X	
Study Medication Dispensing	X	X	X	X		
Contraceptive Use Documentation	X	X	X	X	X	X
Joint Count (28)	X	X	X	X	X	
Patient Assessment of Arthritis Pain	X	X	X	X	X	
Patient Global Assessment of Arthritis	X	X	X	X	X	
Physician Global Assessment of Arthritis	X	X	X	X	X	
HAQ-DI	X	X	X	X	X	
SF-36 (Version 2, Acute)		X			X	
EuroQol EQ-5D		X			X	
Work Productivity and Activity Impairment (WPAI) Questionnaire		X			X	
Safety Assessment/ AE Reporting	X	X	X	X	X	X
Concomitant Medication Review	X	X	X	X	X	X
End of Study Assessment					X	

^a Re-testing of abnormal laboratories may be required (see Section 7.15).

^b Month 12 visit only.

^c Pregnancy tests may also be repeated as per request of IRB/IECs or if required by local regulations.

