2.2.1. Safety Endpoints

The safety endpoints will be collected and analyzed for all subjects in the study, through the end of the study.

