6.3. Visit 1, Baseline Visit (Day 1)

Subjects are required to fast for at least 6 hours prior to the visit. Subjects who have met all the inclusion criteria and have no exclusion criteria present may participate in the study.

Procedures that will be performed prior to the first dose of study drug include:

- Physical assessment including assessment of new physical findings, weight and vital signs.
- Review of inclusion/exclusion criteria.
- Fasting laboratory testing including blood chemistry, hematology, CRP, lipid profile.
- Pregnancy testing must be completed for all women of child-bearing potential: all subjects must test negative; confirmation and documentation of the use of a highly effective method of contraception by sexually active subjects of child-bearing potential must be done (for Canada, please refer to [Appendix 6](#) for specific contraception requirements).

- Banked biospecimen sample.
- 28 tender /painful and swollen joint counts.
- Completion of the following assessments:
 - Patient assessment of arthritis pain.
 - Patient global assessment of arthritis.
 - Physician global assessment of arthritis.
 - HAQ-DI.
 - SF-36 (Version 2, Acute).
 - EuroQol EQ-5D.
 - Work Productivity and Activity Impairment (WPAI) Questionnaire.
- Safety Assessment and AE Reporting.
- Concomitant Medication Review.
- Confirm that all screening procedures have been completed and the subject is eligible for randomization.
- Randomize and dispense study medication as identified by the randomization/drug dispensing system.
- Schedule the subject to return for Visit 2 (Month 2).

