9.2. Safety Analysis

9.2.1. Analysis of Primary Safety Endpoint

The co-primary safety endpoints of malignancies and MACE will be analyzed to provide comparative rates for tofacitinib vs. the combined TNFi.

The primary statistical safety objective is the estimation of the hazard ratios relative to the TNFi control for the two tofacitinib doses combined and for each dose of tofacitinib separately for the adjudicated events of MACE and malignancy excluding non-melanoma skin cancer. Analysis of the primary safety endpoints will be based upon adjudicated events.

Hazard ratios for the safety events of main interest will be calculated separately for each primary endpoint. The ratios for both tofacitinib doses combined versus the control, for each tofacitinib dose versus the control, and for the two tofacitinib doses versus each other will be reported along with their 95% confidence intervals. Adjustments for multiplicity will not be applied.

The primary statistical method for deriving estimators for hazard ratios will be the fitting of proportional hazards (Cox) regression models. A model containing only the single independent variable for treatment group will be calculated and reported. The effects of adding other predictors to the model, such as geographic region, age, gender, and so forth will be fully explored and reported. An analysis by TNFi subset strata (ie, the sites/regions where either adalimumab or etanercept was used) will be conducted to assure consistency of results.

A Surveillance, Epidemiology, and End Results (SEER) analysis of the malignancy endpoint will be conducted.

Both total time (or ITT) and on treatment analyses of the main safety endpoints will be conducted. The total time analysis will not censor times to event and will ascribe events to randomized treatment.

The on-treatment analysis for MACE will censor subjects who crossover from tofacitinib, adalimumab or etanercept to standard of care at 60 days after standard of care is initiated. The principal analysis for malignancies will not censor for subjects crossing to standard of care (ie, will be the total time analysis).

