5.4. Treatment Misallocations

For subjects with errors in treatment allocation, described below is the convention under which treatment groups they will be reported for efficacy and safety analyses:

If a subject was:

- Randomized but not treated, then the subject will be excluded from all analyses according to the definitions of FAS, Per Protocol, and Safety Analysis Sets given just above.
- Randomized but took incorrect treatment, then the subject will be reported under his/her randomized treatment group for all analyses based on FAS (or Safety Analysis Set), but will be omitted from analyses based on Per Protocol Analysis Set.

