5.5.2. Deviations Assessed Post-Randomization

The deviation resulting in exclusion from the safety analysis set and the full analysis set is failure to take any study medication.

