7.1.1. Censoring Time for Time-to-event

There are three ways in defining the time to an event:

- The “60-Day On-Treatment Time” is the time from first study dose to an event observed while a subject is exposed to the study treatment plus the applicable attribution window. The 60-Day On-Treatment Time analysis will censor subjects who cross over from tofacitinib or TNFi to standard of care at 60 days after the last dose of randomized study drug.
- The “Total Time” is the time from first study dose to an event regardless whether the event occurs during on-treatment period or after the subject discontinues the study treatment and is still being followed. The Total Time analysis will not censor subjects who cross over from tofacitinib or TNFi to standard of care and will ascribe events to randomized treatments.
- The “28-Day On-Treatment Time” is the time from first study dose to an event observed while a subject is exposed to the study treatment plus the applicable attribution window. The 28-Day On-Treatment Time analysis will censor subjects who cross over from tofacitinib or TNFi to standard of care at 28 days after the last dose of randomized study drug.

More specifically, in time-to-event analyses for a given event, a subject’s time to event will be considered censored if any of the following conditions occurs prior to the subject experiencing the event in question:

- The subject is lost to follow-up (censoring time = study day of last on-study contact, eg, last visit, last lab test, and the like).
- The subject withdraws consent (censoring time = study day of last on-study contact).
- The subject is in the study under the protocol at the declared end of the study (censoring time = study day of last on-study contact).
- The subject dies without having experienced the event of interest (censoring time = study day of death).

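### The protocol promises a total-time ITT analysis of all subjects, but no SAP analysis set contains the randomised subjects who never took a dose

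*Protocol*

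**What the plan says.** The protocol describes the population and the total-time analysis without any dosing condition:

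- Protocol Summary, Safety Analysis: "The safety analysis will include all subjects in the study". The same section says that "Both total time (ITT) and on treatment analyses of the main safety endpoints will be conducted".
- Protocol 2.2.1: "The safety endpoints will be collected and analyzed for all subjects in the study, through the end of the study".
- Protocol 9.2.1 repeats the ITT label and adds: "The total time analysis will not censor times to event and will ascribe events to randomized treatment".

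The SAP requires a dose throughout:

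- SAP 5.1 and 5.3 limit both the Full Analysis Set and the Safety Analysis Set to randomised subjects with at least one dose. SAP 5.2 draws the Per Protocol set from the Full Analysis Set.
- SAP 5.4: "Randomized but not treated, then the subject will be excluded from all analyses". SAP 5.5.2 agrees: "The deviation resulting in exclusion from the safety analysis set and the full analysis set is failure to take any study medication".
- SAP 7.1.1: Total Time "is the time from first study dose to an event regardless whether the event occurs during on-treatment period".
- SAP 8.2.1 runs the primary analysis on the Safety Analysis Set. Its listed robustness checks use that set or the Per Protocol set.

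On timing, Protocol 6.3 lists this step among the procedures done before the first dose: "Randomize and dispense study medication as identified by the randomization/drug dispensing system". Protocol 5.2 says that supplies are open-label, with drug and dose on the label.

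**The concern.** Leaving out never-dosed subjects does no harm when the decision not to start cannot depend on the arm, as under effective blinding. Here the subject and the site know the arm before the first dose, and the choice is between tablets and self-injection. A subject who draws the less welcome option can decline to start, and refusers may differ in baseline risk from those who start.

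SAP 4.2 bases the malignancy decision on Total Time, against 1.8 for tofacitinib versus TNFi and 2.0 for 10 mg versus 5 mg. For MACE, Total Time is the uncensored counterpart of the on-treatment analysis. In both roles a reader of the protocol would take it as the analysis that keeps the full randomised comparison, and the SAP definition does not quite do that. The primary MACE analysis counts time on treatment plus 60 days. A dose is inherent in it, so it is not at issue.

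**Working it through.** **Step 1: the plan's own event numbers.** Inputs from Protocol 9.1 and section 3: margin 1.8, true hazard ratio 1.0, two-sided 95% confidence, 90% power (malignancy) and 80% (MACE), and 1:1:1 allocation, hence 2:1 for combined tofacitinib versus TNFi. The Schoenfeld formula is

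events = (z for confidence + z for power)² / [(2/3)(1/3)(ln 1.8)²].

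It gives 136.86, rounded up to 137, for malignancy (stated 138) and 102.23, rounded up to 103, for MACE (stated 103). The plan's figures reproduce, and nothing here disputes them.

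**Step 2: the pass boundary.** At 138 malignancies, SE of log HR = 1/√(138 × 2/9) = 0.181. The upper 95% limit is below 1.8 only if the observed hazard ratio is below 1.8 × exp(-1.96 × 0.181), about 1.26.

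**Step 3: the shift in the hazard ratio.** The documents do not say how many subjects were never dosed, so what follows is an assumption. Let a fraction u of the TNFi arm, and nobody in the tofacitinib arms, never start, with k times the event rate of TNFi subjects who do. The all-randomised TNFi rate is then (1 - u + uk) times the dosed rate, so

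dosed-only HR / all-randomised HR = 1 - u + uk.

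With 4000/3, about 1333 per arm, 1% to 3% is 13 to 40 subjects.

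| u | k = 0.5 | k = 1 | k = 2 | k = 3 |
|---|---|---|---|---|
| 1% | 0.995 | 1.00 | 1.01 | 1.02 |
| 3% | 0.985 | 1.00 | 1.03 | 1.06 |

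The range is -1.5% to +6%, and the shift is zero when refusers carry average risk.

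**Step 4: the effect on the malignancy decision.** If the all-randomised hazard ratio is 1.8, the chance that the dosed-only upper limit falls below 1.8 is Φ(-1.96 - ln(ratio)/0.181):

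- Ratio 1.00: 2.5%.
- Ratio 0.985 (3% undosed, half the risk): Φ(-1.96 + 0.0837) = about 3.0%.
- Ratio 1.03 (3% undosed, twice the risk): about 1.7%.
- Ratio 1.06 (3% undosed, three times the risk): about 1.1%.

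Dropping high-risk TNFi subjects lowers the TNFi rate that remains and raises the dosed-only hazard ratio, which makes passing harder. The SE of 0.181 assumes a 2:1 event split. At a true ratio of 1.8 the split is 3.6:1 and the SE about 0.206; the 3.0% is unchanged to one decimal.

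**Step 5: power.** With the protocol's enrolment, dropout and event rates, about 135.5 malignancies are expected in 5 years. If 0.5% to 3% of all 4000 subjects (20 to 120) were undosed, the one-dose rule would remove about 0.7 to 4.1 of them. Malignancy power would go from 0.902 to between 0.901 and 0.894. Power is not the issue.

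**The case against.** The other side has several fair points.

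- **The number is probably small.** Subjects must be willing to follow the treatment plan (Protocol 4.1, criterion 9). Those with prior failure of, or a contraindication to, the local TNFi are excluded (4.2, criterion 8d). Drug is handed out at the randomisation visit. This stands: the size is unknown and may be negligible.
- **A one-dose safety set is conventional and was chosen early.** The SAP amendment log records the choice before enrolment began, so it was not driven by data. That stands as to motive. It does not make the analysis ITT.
- **The SAP may modify the protocol.** Protocol section 9 allows this, but major changes to the primary analysis must also appear in a protocol amendment. The current protocol, at Amendment 8, still carries the all-subjects and ITT wording.
- **The protocol never defines ITT as all randomised.** True, and the label may have been meant only as a contrast with on-treatment censoring. Even so, nothing in the protocol limits the analysis to dosed subjects.
- **There may be little to analyse.** Protocol 8.2 starts CRF recording of adverse events at the first dose, although serious events are reportable from consent. This limits what the remedy can show.

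A reader might also infer that no planned output would reveal the problem. That goes too far. SAP 5.5.2 treats taking no drug as a deviation, SAP 5.5 lists potentially important deviations in the study report, and a disposition table is planned. What the documents do not promise is a count of never-dosed subjects by arm with reasons.

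**Conclusion.** The conflict between the documents is real: the protocol claims an all-subjects ITT analysis and the SAP contains none. Because the arm is known before dosing, the gap could in principle bias the malignancy hazard ratio and the supportive Total Time MACE analysis.

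The likely size is small. Under the assumption of 1% to 3% undosed in the TNFi arm only, at 0.5 to 3 times the risk, the hazard ratio shifts by -1.5% to +6%. Such a shift matters only for a result near the boundary of about 1.26.

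A reader might infer that the exclusion substantially raises the chance of a false non-inferiority finding. The documents do not support that. In the TNFi-refusal scenario high-risk refusers work against passing, and low-risk refusers raise the malignancy false-pass rate only to about 3.0%. A larger rise would need high-risk subjects to refuse tablets while nobody refused injections, and nothing in the plan suggests this. In addition, SAP 4.2 requires both malignancy and MACE to pass, so a malignancy-only rate is not the rate of false overall conclusions.

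The point is worth correcting because the remedy is cheap, not because the trial's conclusion is shown to be at risk.

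**What to change.** 1. In SAP 5, define an all-randomised set, analysed by randomised arm with the clock starting at randomisation.
2. In SAP 8.2.1, add the Total Time Cox model for both co-primary endpoints on that set as a robustness analysis, using whatever follow-up never-dosed subjects have. The existing primary analyses stay as they are.
3. Tabulate never-dosed subjects by arm, with the reason and the length of follow-up. A bound that assigns assumed event rates to those without follow-up is optional, since any multiplier would be arbitrary.
4. Reconcile the wording of the Protocol Summary, Protocol 2.2.1 and 9.2.1 with the SAP, so that a dosed-only analysis is not called ITT or said to cover all subjects. In the same edit, settle whether the Safety Analysis Set groups subjects by treatment received (SAP 5.3) or by randomised arm (SAP 5.4).

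The cost is some wording, one extra model per endpoint and one table. The downside is that never-dosed subjects may have little recorded follow-up, so the added analysis may differ little from the existing one. In that case the table by arm carries most of the information.
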